9.3.2. Exclusion Criteria

Participants meeting any of the following criteria will not be eligible for enrollment in this study:

1. Current participation in an investigational clinical trial or expanded access program in which the participant may be receiving Oxbryta® (Voxelotol).
2. Medical, psychological, or behavioral condition that, in the opinion of the study doctor, would confound or interfere with evaluation of safety and/or effectiveness of the study drug, prevent compliance with the study protocol, preclude informed consent; or render the participant unable/unlikely to comply with the study procedures.

9.4. Variables

| Variable | Role | Data source(s) | Operational definition |
|-------------------------------|--|------------------|--|
| Index date | Study period | Case report form | Inform consent date |
| Index year | Study period | Case report form | Inform consent date |
| Pre-Oxbryta | Study period | Case report form | Baseline: the most recent observation before receiving Oxbryta |
| Post-Oxbryta | Study period | Case report form | Follow up period up to 5 years |
| End of Treatment | Study period | Case report form | Captured from end of treatment form |
| End of Study | Study period | Case report form | Captured from end of study form |
| Age | Demographics | Case report form | Age at index year |
| Sex | Demographics | Case report form | Captured from the inform consent and eligibility form |
| Race/Ethnicity | Demographics | Case report form | Captured from the inform consent and eligibility form |
| SCD genotype | SCD disease history | Case report form | Captured from SCD disease history form |
| Hydroxyurea use | SCD disease history | Case report form | Captured from SCD disease history form |
| Height | Baseline characteristics | Case report form | Captured from Physical examination form |
| Weight | Baseline characteristics | Case report form | Captured from Physical examination form |
| Pre-Oxbryta SCD complications | Medical history | Case report form | Captured from Pre-Oxbryta treatment form |
| Concomitant Medications | Concomitant Medications | Case report form | Captured from concomitant medications form |
| Hemoglobin | Effectiveness endpoint measures - Hematology | Case report form | Captured from laboratory assessment-Hematology form |
| Reticulocyte count (%) | Effectiveness endpoint measures – Hematology | Case report form | Captured from laboratory assessment-Hematology form |
| Reticulocyte count | Effectiveness endpoint | Case report form | Captured from laboratory |

| Variable | Role | Data source(s) | Operational definition |
|--|--|------------------|---|
| (absolute) | measures – Hematology | | assessment-Hematology form |
| White blood cells (WBC) | Effectiveness endpoint measures – Hematology | Case report form | Captured from laboratory assessment-Hematology form |
| Absolute neutrophil count (ANC) | Effectiveness endpoint measures – Hematology | Case report form | Captured from laboratory assessment-Hematology form |
| Mean corpuscular volume (MCV) | Effectiveness endpoint measures – Hematology | Case report form | Captured from laboratory assessment-Hematology form |
| Mean corpuscular hemoglobin concentration (MCHC) | Effectiveness endpoint measures – Hematology | Case report form | Captured from laboratory assessment-Hematology form |
| Platelets | Effectiveness endpoint measures – Hematology | Case report form | Captured from laboratory assessment-Hematology form |
| Aspartate Aminotransferase (AST) | Effectiveness endpoint measures – Hematology | Case report form | Captured from laboratory assessment-Hematology form |
| Alanine Aminotransferase (ALT) | Effectiveness endpoint measures – Hematology | Case report form | Captured from laboratory assessment-Hematology form |
| Lactate Dehydrogenase (LDH) | Effectiveness endpoint measures - Hematology | Case report form | Captured from laboratory assessment-Hematology form |
| Bilirubin (Total) | Effectiveness endpoint measures - Chemistry | Case report form | Captured from laboratory assessment-Chemistry form |
| Bilirubin (Direct) | Effectiveness endpoint measures - Chemistry | Case report form | Captured from laboratory assessment-Chemistry form |
| Bilirubin (Indirect) | Effectiveness endpoint measures - Chemistry | Case report form | Captured from laboratory assessment-Chemistry form |
| Creatinine | Effectiveness endpoint measures – Chemistry | Case report form | Captured from laboratory assessment-Chemistry form |
| Ferritin | Effectiveness endpoint measures – Chemistry | Case report form | Captured from laboratory assessment-Chemistry form |
| Iron | Effectiveness endpoint measures – Chemistry | Case report form | Captured from laboratory assessment-Chemistry form |

| Variable | Role | Data source(s) | Operational definition |
|--|--|------------------|---|
| Serum cystatin C | Effectiveness endpoint measures – Chemistry | Case report form | Captured from laboratory assessment-Chemistry form |
| Total Iron Binding Capacity (TIBC) | Effectiveness endpoint measures – Chemistry | Case report form | Captured from laboratory assessment-Chemistry form |
| T2*MRI | Effectiveness endpoint measures – Chemistry | Case report form | Captured from laboratory assessment-Chemistry form |
| Urine Albumin | Effectiveness endpoint measures – Renal function | Case report form | Captured from laboratory assessment- Renal function form |
| Urine Creatinine | Effectiveness endpoint measures – Renal function | Case report form | Captured from laboratory assessment- Renal function form |
| Albumin Creatinine Ratio (ACR) | Effectiveness endpoint measures – Renal function | Case report form | Captured from laboratory assessment- Renal function form |
| Hemoglobinuria | Effectiveness endpoint measures – Renal function | Case report form | Captured from laboratory assessment- Renal function form |
| GFR | Effectiveness endpoint measures – Renal function | Case report form | Captured from laboratory assessment- Renal function form |
| Transfusions | Safety endpoint measures | Case report form | Captured from transfusions form |
| Healthcare Resource Utilization | Effectiveness endpoint measures | Case report form | Captured from Healthcare Resource Utilization form |
| PROMIS | Effectiveness endpoint measures | Case report form | Captured from PROMIS form |
| Patient Global Impression of Change (PGI-C) | Effectiveness endpoint measures | Case report form | Captured from Patient Global Impression of Change (PGI-C) form |
| Clinical Global Impression of Change (CGI-C) | Effectiveness endpoint measures | Case report form | Captured from Clinical Global Impression of Change (CGI-C) form |
| Pain Scale | Effectiveness endpoint measures | Case report form | Captured from Pain Scale form |
| Sheehan Disability Scale | Effectiveness endpoint measures | Case report form | Captured from Sheehan Disability Scale form |
| Exercise Tolerance | Effectiveness endpoint | Case report form | Captured from Exercise |

| Variable | Role | Data source(s) | Operational definition |
|----------------------------------|--------------------------|------------------|--|
| | measures | | Tolerance form |
| Pregnancy Testing and Fertility | Safety endpoint measures | Case report form | Captured from Pregnancy Testing and Fertility form |
| SCD Complications/Adverse Events | Safety endpoint measures | Case report form | Captured from SCD Complications/Adverse Events Question form |
| Pregnancy | Safety endpoint measures | Case report form | Captured from Pregnancy Notification and Outcome forms |
| Oxbryta Physician Administration | Exposure measures | Case report form | Captured from Oxbryta Physician Administration form |
| Oxbryta Participant Adherence | Exposure measures | Case report form | Captured from Oxbryta Participant Adherence form |

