7. RATIONALE AND BACKGROUND

This noninterventional study is designated as a PASS and is conducted voluntarily by Pfizer.

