9.11.3. Effectiveness Endpoint Measures Analyses

Baseline Demographic Characteristics:

Baseline demographic characteristics will be summarized descriptively.

Endpoints:

- Change from pre-Oxbryta® (Voxelotor) treatment period in Hb, hemolysis measures, measures of iron overload, and renal function over time will be summarized descriptively.
- Annualized rate of significant SCD-related clinical events, for example VOC, ACS, priapism, stroke, TIA, chronic or end stage kidney disease, iron overload, leg ulcers, cardiac malfunction, and PH will be calculated. The association between change in Hbhemolysis marker and rates of SCD-related clinical events will be evaluated.
- Rates of outpatient visits (including infusion center, acute care, or telemedicine visit), ED visits, hospitalizations, acute and chronic RBC transfusions, home oxygen supplementation, and renal dialysis will be summarized with a similar approach as incidences of SCD-related clinical events. The total cost associated with clinical interventions will be summarized descriptively.

- HRQoL measures over time will be summarized descriptively. Proportions of participants with improved HRQoL measures will be calculated and the associated 95% Clopper Pearson Exact confidence intervals will be constructed as appropriate.
- Rates of SCD-related clinical events, healthcare resource utilization, total cost associated with clinical interventions (if available) and HRQoL while on Oxbryta® (Voxelotor) treatment will be compared with the corresponding measures prior to the first dose of Oxbryta® (Voxelotor) treatment, as appropriate.

Subgroup analysis:

Similar comparisons may be performed between the subgroup of participants who discontinue Oxbryta® (Voxelotor) treatment but remain in the study and those participants who remain on Oxbryta® (Voxelotor).

Other subgroup or sensitivity analyses may be performed.

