9.11.4. Safety Analysis

SAEs and protocol-specified AEs will be classified according to Medical Dictionary for Regulatory Activities (MedDRA). The frequency of AEs will be tabulated by system organ class, preferred term, severity, and relationship to Oxbryta® (Voxelotor) treatment.

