4.7. Statistical methodology and analyses

The following general analysis will be followed for this study, unless otherwise specified.

Unless otherwise specified, continuous/quantitative variables will be summarized using descriptive statistics which will include the number of participants with data to be summarized (n), mean, standard deviation (SD), median, first and third quartile (Q1, Q3), minimum, maximum, and the number of missing observations. Minimum and maximum will be reported with the same number of decimal places as collected in raw data, while mean, median, Q1, Q3 will be reported with one extra decimal place, and SD will be reported with two extra decimal places. Descriptive statistics for categorical/qualitative variables will be presented with number of participants and percentage (%) of participants in each category.

Percentages will not include the missing category and will be calculated over the number of participants with available (non-missing) data. A category with a zero count will be presented as “0” and a category with a 100 percentage will be displayed as “100”.

The annualized incidence rate is defined as total numbers of a given event for all participants divided by the total patient-year where the total patient-year is defined as the sum of total duration (years) as defined in the Section 4.7.1 for all participants.

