4.7.3. Analyses for Effectiveness Endpoint Measures

Since this study was not designed as the efficacy study for different indications that contribute significant information about product safety, the analyses in the SAP are considered fit-for-purpose for an abbreviated clinical study report with data scope including 1) full safety data and 2) limited efficacy data to support the benefit-risk evaluation.

Given the reporting nature of the PROMIS items, the reported PRO response was sparse. Therefore, they were excluded from the planned CSR analyses.

The analyses for effectiveness endpoints are based on full analysis set (Section 4.2). The analyses for the abbreviated CSR focus on hematologic and renal function laboratory parameters and SCD-related clinical events.

Participant disposition, non-SCD medical history, concomitant medication, study drug administration (including dosage changes initiated by the participant and by the physician), demographics and baseline characteristics will be summarized descriptively based on full analysis set.

The descriptive statistics will be provided for the following medications:

- long-acting opioids
- Erythropoiesis-stimulating agents
- Other relevant pain meds (e.g. Gabapentin, Lyrica, Cymbalta)
- SCD disease modification agents (hydroxyurea, Adakveo/crizanlizumab, L-Glutamide/levoglutamide).

The study drug administration will be categorized as 1) < 1 month, 2) >=1, <2 months, 3) < 3 months, 4) >=3 months, < 6 months, 5) >=6 months, < 9 months, 6) >=9 months, < 12

months, 7) ≥ 12 months, < 18 months, 8) ≥ 18 months, < 24 months, 9) ≥ 24 months, < 36 months, 10) ≥ 36 months, < 48 months and 11) ≥ 48 months.

The following effectiveness endpoints will be summarized descriptively:

- Change from pre-Oxbryta treatment period in the following hematologic parameters corresponding to treatment with Oxbryta® (Voxelotol):
 - Hb
 - Hemolysis measures, including % reticulocytes, absolute reticulocytes, bilirubin (total, direct, and indirect)
 - ALT and AST

Analysis: Observed and change from pre-Oxbryta treatment period on Hb, Hemolysis measures will be summarized descriptively ([Section 4.7](#)) by visit

If a queried hemolysis value remained greater than its threshold listed in the table below, the value would be deemed erroneous and excluded from the analysis,

Parameter	Threshold
Reticulocyte Count (absolute)	10,000 $10^{9}/L$
Ferritin	100,000 $\mu g/L$

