6. APPENDICES

6.1. Appendix A: List of tables

Table/Listing	Title	Endpoint
Table 15.1.1	Summary of Participant Disposition - Full Analysis Set	Disposition
Table 15.1.2	Demographics and Baseline Characteristics - Full Analysis Set	Baseline
Table 15.1.3	Medical History – Full Analysis Set	Medical history

Table 15.1.4	Study Drug Administration - Safety Analysis Set	Exposure
Table 15.1.5	Study Drug Administration and Dosage Changes Initiated by the Physician - Safety Analysis Set	Exposure
Table 15.2.1	Change in Hematologic Laboratory -Hb Tests by Visit - Full Analysis Set	Effectiveness
Table 15.2.2	Change in Hematologic Laboratory -Hemolysis measures by Visit - Full Analysis Set	Effectiveness
Table 15.2.3	Change in Chemistry Laboratory - Chemistry measures by Visit - Full Analysis Set	Effectiveness
Table 15.2.4	Change in Renal Function Laboratory Tests by Visit - Full Analysis Set	Effectiveness
Table 15.2.5	Summary of SCD Complications-Full Analysis Set	Effectiveness
Table 15.2.5.1	Summary of Transfusions -Full Analysis Set	Effectiveness
Table 15.2.6	Annualized Incidence Rate of SCD Complications - Safety Analysis Set	Effectiveness
Table 15.2.6.1	Annualized Incidence Rate of Transfusions - Safety Analysis Set	Effectiveness
Table 15.2.7	Summary of Patient Global Impression of Change (PGIC) – Full Analysis Set	HRQoL
Table 15.2.8	Summary of Clinical Global Impression of Change (CGIC) – Full Analysis Set	HRQoL
Table 15.3.1	Treatment Emergent Adverse Events by System Organ Class and Preferred Term by Severity - Safety Analysis Set	Safety
Table 15.3.2	Treatment Related Treatment Emergent Adverse Events by System Organ Class and Preferred Term by Severity- Safety Analysis Set	Safety

Table 15.3.3	Treatment Emergent Serious Adverse Events by System Organ Class and Preferred Term by Severity - Safety Analysis Set	Safety
Table 15.3.4	Pregnancy Outcomes and Fertility listings - Safety Analysis Set	Safety
Table 15.3.5	Individual Listings of Deaths- Safety Analysis Set	Safety
Table 15.3.6	Listing of AEs Leading to Discontinuation of the Study - Safety Analysis Set	Safety
Table 15.3.7	Individual Listing of SAEs - Safety Analysis Set	Safety
Table 15.4	Listing of Concomitant Medication - Safety Analysis Set	Concomitant Medication
Table 15.5.1	Annualized Incidence Rate of Acute Pain Crisis – Safety Analysis Set (With Chronic Pain)	Subgroup
Table 15.5.2	Annualized Incidence Rate of Acute Pain Crisis – Safety Analysis Set (Without Chronic Pain)	Subgroup

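### ALT and AST are handled as hematology effectiveness measures with at most a by-visit summary, and no count of marked elevations is planned, so those not reported as AEs or SAEs go uncounted

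*Protocol*

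**What the plan says.** **Role.** The variables table in protocol 9.4 lists "Alanine Aminotransferase (ALT) | Effectiveness endpoint measures – Hematology", and AST has the same role. SAP 4.3 repeats this for both enzymes. In both tables the safety role goes only to transfusions, pregnancy testing and fertility, pregnancy, and SCD complications/AEs. No laboratory test has it.

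**Effectiveness analysis.** Protocol 9.11.3 says that change from the pre-treatment "treatment period in Hb, hemolysis measures, measures of iron overload, and renal function over time will be summarized descriptively"; the enzymes are not named. SAP 4.7.3 lists ALT and AST as a separate bullet under hematologic parameters, but the analysis sentence that follows reads "Observed and change from pre-Oxbryta treatment period on Hb, Hemolysis measures will be summarized descriptively", by visit. SAP 4.7 defines the descriptive set as n, mean, SD, median, "first and third quartile (Q1, Q3), minimum, maximum, and the number of missing observations". The nearest table is 15.2.2, "Change in Hematologic Laboratory -Hemolysis measures by Visit - Full Analysis Set".

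**Safety analysis.** Protocol 9.11.4 plans this: "The frequency of AEs will be tabulated by system organ class, preferred term, severity, and relationship to Oxbryta® (Voxelotor) treatment". SAP 4.7.4 covers SCD complications, TEAEs, SAEs, pregnancy and fertility, and events leading to study discontinuation. Tables 15.3.1 to 15.3.7 follow that list and include no laboratory table.

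**Purpose.** Protocol section 7 states: "This noninterventional study is designated as a PASS and is conducted voluntarily by Pfizer". Safety and tolerability are part of the primary objective in both documents. SAP 4.7.3 describes the abbreviated report as containing "1) full safety data and 2) limited efficacy data to support the benefit-risk evaluation".

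**The concern.** ALT is ordinarily read as a liver-safety test. The question put to such a test is how many people had a marked rise after starting the drug, and what their values were beforehand. A by-visit summary of a continuous variable answers a different question, namely where the distribution sits at each timepoint. Because the enzymes carry an effectiveness role, they fall outside the safety section, and nothing in either document asks the participant-level question.

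What is at stake is the completeness of the safety conclusion. A non-serious rise that nobody wrote up as an AE could be in the database and still be missing from every count in the final report.

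**Working it through.** The documents state no figure on this point, and SAP 4.5 says there is no formal sample size calculation. There is therefore nothing to reproduce. The check is a reading of the text followed by an illustration.

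**Step 1. Is any count of abnormal values planned?** I looked in protocol 9.4, 9.11.3 and 9.11.4, in SAP 4.3, 4.7, 4.7.3 and 4.7.4, and in SAP Appendix A. None contains a multiple of the upper limit of normal (ULN), a laboratory grade, a shift table or an abnormal-value count for ALT or AST.

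**Step 2. How else could an elevation be counted?** Footnote i of protocol Appendix 1 tells sites to record SAEs, AEs of interest, drug-related AEs and other safety events. Those entries reach Tables 15.3.1 to 15.3.3 by preferred term and severity, and SAEs also reach listing 15.3.7. The footnote refers to Section 11 for definitions, but Section 11 gives no list of AEs of interest. A non-serious rise that no one attributed to the drug has no certain route into those tables.

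**Step 3. Are the values there to be counted?** Protocol 10.3.6.1.1 has sites enter all available results from scheduled outpatient visits after treatment start, plus presentation and discharge values from acute visits. For the pre-treatment period only the most recent routine outpatient result is entered.

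**Step 4. What would the planned statistics show?** Assumed inputs, none from the documents: 300 tested at one visit, SD of change 15 U/L, 6 participants (2%) with an extra rise of 200 U/L.

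- Mean: 6 × 200 / 300 = 4.0 U/L.
- Median: about 1% of the sample crosses from below to above it, so the shift is about 0.01 × 15 / 0.399 = 0.38 U/L.
- SD: √(15² + 0.02 × 0.98 × 200²) = √(225 + 784) = 31.8 U/L.
- SD with one affected participant: √(15² + (1/300)(299/300) × 200²) = √(225 + 132.9) = 18.9 U/L.
- Maximum (simulated average): about 200 U/L with one affected participant and about 219 U/L with six.
- Count: 6/300 = 2.0%.

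This places all six rises at the same visit. Protocol Appendix 1 has 12 post-dose timepoints. If the rises fall at different visits, a visit with one of them moves its mean by 200/300 = 0.67 U/L.

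**Step 5. Same question at the planned size.** Assume all 500 are tested and each affected participant rises by 3 × ULN, with no change in the others. The expected number is 500 × p, the mean shift is p × 3, and the chance of at least one case is 1 − (1 − p)^500.

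| Assumed rate p | Expected cases | Chance of at least one | Shift in mean (× ULN) |
|---|---|---|---|
| 0.5% | 2.5 | 0.918 | 0.015 |
| 1% | 5 | 0.993 | 0.03 |
| 2% | 10 | >0.999 | 0.06 |
| 5% | 25 | >0.999 | 0.15 |

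Cases would probably be present even at low rates, while the mean hardly moves.

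**The case against.** **The planned summary is more than a mean.** A reader might infer that only a mean change is planned. SAP 4.7 does not support that, since it also gives the SD, quartiles, minimum and maximum, for both observed values and change. In the illustration the SD more than doubles and separates six cases (31.8) from one (18.9), so a careful reader would notice something. This stands. But an inflated SD or a high maximum does not give the number of participants affected, and neither shows their pre-dose status.

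**AE reporting does count elevations.** A reader might infer that liver-enzyme rises would not be counted at all. The documents do not support that either: those recorded as AEs or SAEs are tabulated, and recording them is an instruction to sites. The requirement in protocol 11.1 for an explicit causal statement governs reports to the sponsor's safety unit, so it does not by itself restrict CRF entry. The gap is confined to rises that never become an AE record.

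**Never-dosed participants.** The Full Analysis Set includes screen failures, and a reader might infer that they dilute the on-drug change. SAP 4.7.1 starts the post-Oxbryta period at first dose, so they have no post-dose change to contribute.

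**Table titles.** No Appendix A title names ALT or AST, but titles there are by category and most other analytes are not named either. The enzymes sit in a bullet just above the by-visit sentence. This is an ambiguity, not proof of omission.

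**No laboratory safety endpoint was promised.** The safety endpoints in protocol 8.1.1.3 and SAP 3.3 are SAEs, AEs of interest, AEs leading to dose modification or discontinuation, and pregnancy outcomes and fertility. Nothing in the documents names liver injury as a known concern. A reader should not infer a documented liver signal, nor a breach of a stated endpoint.

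**A count has weaknesses of its own.** Testing is per standard of care, ULN is not among the listed variables, ages start at 4, laboratories are local, and there is no control group. A post-dose maximum that includes acute visits is not comparable with a single routine baseline value. All of this stands and shapes the fix.

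**Conclusion.** The point holds in this form: ALT and AST have an effectiveness role in both documents, their by-visit summary is not clearly specified, and no participant-level count of marked elevations is planned. Rises not reported as AEs or SAEs would therefore go uncounted in a PASS whose report is said to hold full safety data.

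The size cannot be derived from the documents. Under the assumed scenario, the mean moves 4.0 U/L, the median about 0.4 U/L and the SD from 15 to about 32, and none of them yields the 6/300 (2.0%) that a count gives. The conclusion does not depend on those particular inputs, because summary statistics of location and spread do not report a number of people.

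This is a worthwhile, inexpensive improvement to the safety reporting. It does not invalidate the planned AE analyses.

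**What to change.** 1. In protocol 9.4 and SAP 4.3, give ALT and AST a safety role. In SAP 4.7.3, state that the by-visit sentence covers them.
2. In protocol 9.11.4 and SAP 4.7.4, add one table on the Safety analysis set: the number and percentage of tested participants whose highest ALT, and separately AST, from first dose to end of treatment +28 days exceeds prespecified cut-offs. Multiples of 3 and 5 times ULN are examples; if local ULN is not collected, use fixed U/L values. The +28 days matches the SAP's own TEAE window.
3. In the same table show pre-dose status, the number tested and tests per participant.
4. Present scheduled outpatient values separately from acute-visit values, because the entered baseline is a single routine outpatient result.
5. Read ALT first, since AST can also rise with hemolysis.

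**Cost.** One table from values already entered on the CRF, with no new data collection. The counts will depend on how often people were tested, and with no control group they cannot be attributed to the drug. They should be labelled descriptive. Fixed U/L cut-offs, if needed, are a rough tool across children, adults and local laboratories, and the table should say so.
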